6.2 General Methodology

6.2.1 Overview

The analysis described in this SAP will be conducted by Medtronic statisticians. Prior to evaluation of the study's primary objectives, a descriptive analysis will be performed: demographic and other key baseline characteristics, attrition, follow-up experience, adverse events (AE's), and study deviations will be summarized by randomization group for the ITT dataset. All data will be reported; data that is not used for the analysis of objectives, such as data from subjects that were not randomized, will be summarized separately. Additional exploratory analyses may be conducted as deemed appropriate. Subgroups will be considered, which include age, gender, body height, heart failure etiology, LVEF, NYHA class, and QRS duration. Statistical tests will be two sided with alpha = 0.05 unless stated otherwise. Where applicable, absolute and relative effect sizes will be reported.

[figure not shown]
The expected mortality rate from subjects in Mid-Q Response is 4%, so we expect 4% of NYHA values at 12-month follow-ups, as well as a few less at 6-month and 3-month visits, to be missing for subjects who have died while under study. In these cases, the NYHA value will be set to "class V", and treated as being a level of heart failure more severe than NYHA class IV for purposes of all objectives.

6.2.2 Primary Objective: Compare Percent of Subjects with Clinical Composite Score Improvement from Baseline to 6 Months

6.2.2.1 Endpoint Definition

The primary endpoint for the study will be the Clinical Composite Score (CCS) at 6 months (Packer, 2001). The CCS classifies patients according their clinical status at 6 months post-randomization into categories Improved, Unchanged, and Worsened. A patient is classified Worsened in case of death, hospitalization for worsening heart failure, worsened NYHA class (using last observation carried forward), or worsened status on the Global Assessment Score. Also, patients that exit the study or cross over because of worsening heart failure are classified Worsened. A patient is classified Improved when not Worsened and there is an improvement in NYHA class or Global Assessment Score. Patients that are not Worsened or Improved are Unchanged including all patients with missing NYHA class and Global Assessment Score data who are not classified Worsened because of death, HF hospitalization, exit or crossover (see flowchart in Figure 2 below). The main analysis will look at the percentage of patients with Improved CCS.

6.2.2.2 Figure 2: Clinical Composite Score Flowchart

6.2.2.3 Hypothesis

The null-hypothesis that will be tested is that the proportion of patients with Improved CCS is not different between the randomized arms:

$$H_0 : p_{on} = p_{off}$$

$$H_a : p_{on} \neq p_{off}$$

The analysis will use a Chi-square test comparing the proportion improved between randomized arms. The null hypothesis will be rejected if the p-value is < 0.05. It will be concluded that aCRT ON causes a higher proportion of subjects improved in case the null hypothesis is rejected and the proportion Improved is higher in the aCRT on arm.

6.2.2.4 Analysis Methods

Subjects' CCS will be classified according to the algorithm described in Figure 2 and section 6.2.2.1. All subjects' 6-month visits will contribute to the 6-month CCS assessment regardless of when they occur relative to the protocol-defined windows (183 to 223 days from randomization). Non-missing values for dates of death, exit or crossover due to worsening heart failure, or a heart failure event that occur within the interval of 0 to 182 days post-randomization will necessarily lead to a CCS value of 'Worsened' and therefore a value of non-improvement for the primary outcome variable. To be

considered as endpoint events, crossovers and study exits must be indicated on the following respective crossover and exit CRF fields:

Was this an intentional crossover due to worsening heart failure NO YES

Was the exit due to worsening heart failure NO YES

NYHA and patient global assessment scores at 6 months will be used for subjects when available, and will be carried forward from the month 3 visit if this data is not available from the 6 month visit. For subjects having neither a 3-month or a 6-month classification, the baseline value will be carried forward (thus leading to a CCS of 'Unchanged' and a primary outcome value of non-improvement).

SAS code for the derivation of the CCS at 6 months, taken from the AdaptResponse study, is available under separate cover, shortened and with modifications made to reflect differing 6-month visit windows in Mid-Q Response.

The main analysis will use a Chi-square test comparing the binary proportion of subjects classified as improved (e.g., the proportion not worsened and not unchanged) between randomized arms. The null hypothesis will be rejected if the two-sided p-value is < 0.05. In the event this occurs, and the point estimate of the proportion improved in the aCRT ON group is higher compared to the aCRT OFF group, it will be concluded that aCRT ON causes a higher proportion of subjects classified as improved. The following SAS code provides an example of what may be used for this analysis:

```
proc freq data = analysis.PrimaryObj;
table aCRT_ITT*CCS_Improved/chisq nocol nopercents riskdiff;
run;
```

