## **8.9. Scheduled follow-up visits**

After receiving randomization notice via the randomization CRF, Medtronic will provide the target dates and windows for each follow-up visit to the implanting center via the randomization CRF. Follow-up visit windows open on the Window Start date and remain open as defined below. It is recommended that subjects are scheduled as close as possible to the target date for a given follow-up visit.

Should a subject visit fall outside the pre-specified window, a Study Deviation must be reported, and the original follow-up schedule maintained for subsequent visits. Data analyses include follow-up visits, regardless of whether the visit occurs within the window. Therefore, an early or late visit is preferred over a missed visit, but still must be accompanied by a deviation. Follow-up visit windows are listed in Table 3 and are based on days post-randomization.

Required visits post-randomization include follow-up visits at 3 months, 6 months, and 12 months as shown in Figure 2. During these visits information will be collected about adverse events (AE), Cardiovascular (CV) medications, and Heart Failure (HF) assessment, as well as additional information and procedures which vary by visit (see Table 4). Quality of Life (QoL) and Health outcome will be addressed using the KCCQ questionnaire, which subjects will complete during applicable study visits. Full device interrogation (interrogate ALL) data will be collected for subjects at the end of the visit (final interrogation) and a copy of the interrogation files (Save-to-Disk, S2D) must be sent to Medtronic, with a copy also being maintained at the center in the subject's file.

Figure 2: Visit Timelines

The post-randomization follow-up windows are provided in Table 6.

Table 6 post-randomization follow-up windows

Study Follow-up Visit	Window (Calculated days post-randomization)		
	Window Start (days post-randomization)	Target (days post-randomization)	Window End (days post-randomization)
3 Month follow-up	77	91	105
6 Month follow-up	183	183	211
12 Month follow-up*	365	365	393

\*12 Month follow-up visit in the second half of the window is preferred but not required

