6.2.2.9 Sensitivity Analysis 3: Effect from Out of Window Visits

As stated in the CIP, data analyses include follow-up visits, regardless of whether the visit occurs within the window. However, in the presence of many subjects having late visits, the classification of the primary endpoint as a 6-month outcome becomes less accurate. Therefore, a description of visit compliance and a summary of actual days to 6 month assessments will be performed by treatment group. If a Wilcoxon test shows an imbalance in days from randomization to 6 month assessments between aCRT ON and aCRT OFF, or if > 20% of subjects from either study arm have late 6-month visits, one further sensitivity analysis will be performed. In this analysis, CCS will be calculated as above, except that for subjects who have 6 month visits occurring after the visit window has closed (i.e., 224 or more days after randomization), the NYHA and Global Assessment scores used in determining CCS will be carried forward from the baseline or 3 month visit, as available. If a subject's 6 month visit is late and out of window, and they have no post-randomization NYHA or Global Assessment Score data to carry forward, they will be assigned a score of "Unchanged" in the absence of any events that would lead to them being classified as "Worsened". This sensitivity analysis will mirror the main ITT analysis, with ITT assignments for treatment, and using a Chi-square test with two-sided alpha = 0.05 to determine whether the alternative formulation of CCS is associated with treatment, as exemplified in the following SAS code:

```
*** Primary objective - sensitivity analysis #3;
proc freq data = analysis.PrimaryObj;
table aCRT_ITT*CCS_Improved_inWind/nocol nopercnt chisq;
run;
```

Differences observed between this analysis and the main ITT analysis of the primary endpoint can provide evidence about the main endpoint's sensitivity to being measured within the protocol-defined visit windows.

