6.8 Changes to Planned Analysis

Additional details on analysis methods have been added to this SAP, but no changes to the methods defined in the Mid-Q Response CIP version 1 are noted. Future revisions of the Mid-Q response SAP may occur, but deviations from the Mid-Q Response CIP version 1 will require a corresponding CIP revision or, alternatively, a description in the final report, along with the rationale for the deviation. Likewise, deviation from this SAP in the analysis methods of any pre-defined objectives will be documented and explained in the final report.

7. Determination of Sample Size

Sample size calculations were performed to find the number of enrollments required such that a Pearson's chi-squared test with two-sided $\alpha = 0.05$ would have $>80\%$ power when 75% of subjects assigned to aCRT ON and 55% of subjects assigned to have aCRT OFF have improved CCS at six months after randomization. Over the first six months of study, a crossover rate of 3% between both treatment groups is assumed. Given these constraints, it was determined that 220 subjects would need to be randomized, and assuming an attrition rate of 5% from baseline to 6-months post-randomization, **a total of 232 subjects will need to be enrolled in the Mid-Q Response study**. Rationale regarding the estimates for treatment group success rate, control group success rate and six-month crossover rates is provided in the Mid-Q Response CIP. Sample size was estimated by simulation in SAS version 9.4, and independently verified using a simulation in R version 3.4.3. The R code for the sample size calculation is provided under separate cover.

8. Validation Requirements

Verification of analysis of the study's primary objective will be completed with level I validation (independent programming). Secondary and ancillary objectives will be validated with a minimum of level II validation. Analyses that are not related to primary objectives or ancillary endpoints will be validated at a minimum of level II validation if being presented externally in an abstract or publication.

9. References

1. Allison P. "For Causal Analysis of Competing Risks, Don't Use Fine & Gray's Subdistribution Method". *Statistical Horizons Blog*, March 24, 2018. <https://statisticalhorizons.com/for-causal-analysis-of-competing-risks>

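### The SAP closes the 6-month visit window on day 223 and the protocol on day 211, so Sensitivity Analysis 3 counts some protocol-late visits as on time

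*SAP*

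**What the plan says.** Protocol section 8.9, Table 6, lists the window start, target and end in days after randomization: "6 Month follow-up 183 183 211". The text above the table adds: "Should a subject visit fall outside the pre-specified window, a Study Deviation must be reported". Such visits are still analysed.

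SAP section 6.2.2.4 uses every 6-month visit in the Clinical Composite Score (CCS) "regardless of when they occur relative to the protocol-defined windows (183 to 223 days from randomization"). It also says that the CCS program was taken from another study, with "modifications made to reflect differing 6-month visit windows in Mid-Q Response".

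SAP section 6.2.2.9 (Sensitivity Analysis 3) has two alternative triggers. One is a Wilcoxon test showing a between-arm imbalance in days to the 6-month assessment. The other is that more than "20% of subjects from either study arm have late 6-month visits". If either is met, CCS is recalculated. Subjects with "6 month visits occurring after the visit window has closed (i.e., 224 or more days after randomization") then have their NYHA class and Global Assessment carried forward from an earlier visit. The stated aim is to show the endpoint's "sensitivity to being measured within the protocol-defined visit windows".

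The SAP is based on protocol version 1. Section 6.8 states that "no changes to the methods defined in the Mid-Q Response CIP version 1 are noted".

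**The concern.** The SAP does not announce an analysis window of its own. It attributes days 183 to 223 to the protocol, and the protocol in force ends the window on day 211. The limit appears twice in the SAP, as 223 and as 224, so a single typing slip is unlikely.

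Two parts of Sensitivity Analysis 3 depend on it:

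- **The late-visit trigger.** Visits on days 212 to 223 do not count towards the 20%, so the analysis may be skipped when more than 20% of an arm is late by the protocol.
- **The carry-forward rule.** If the analysis runs, NYHA and Global Assessment values from days 212 to 223 are kept. The result then does not show what happens when the endpoint is restricted to the protocol's window, which is its stated purpose.

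**Working it through.** **1. Window lengths (inclusive), from Table 6 and SAP 6.2.2.4**

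| Window | Days | Length |
|---|---|---|
| Protocol, 3 months | 77–105 | 105 − 77 + 1 = 29 |
| Protocol, 6 months | 183–211 | 211 − 183 + 1 = 29 |
| Protocol, 12 months | 365–393 | 393 − 365 + 1 = 29 |
| SAP, 6 months | 183–223 | 223 − 183 + 1 = 41 |

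The SAP's 6-month window does not reproduce from the protocol. The gap is 223 − 211 = 12 days (212 to 223). Day 211 fits the protocol's own pattern of 29-day windows; 41 days matches none of them.

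**2. Trigger count**

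With 220 randomized 1:1, take 110 per arm. Because 22/110 is exactly 20%, exceeding 20% needs at least 23 late visits in an arm. If an arm has L protocol-late visits, the trigger fails in that arm under the SAP limit once at least L − 22 of them fall on days 212 to 223:

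| L | Needed on days 212–223 | Share of L |
|---|---|---|
| 23 | 1 | 4% |
| 28 | 6 | 21% |
| 33 | 11 | 33% |
| 44 | 22 | 50% |

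**3. Chance that this trigger fires in at least one arm**

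The documents give neither a late-visit rate nor a timing distribution, so both inputs are assumptions. Let p be the protocol-late rate, equal in both arms, and s the share of late visits falling on days 212 to 223. Then

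P(fires) = 1 − [P(Bin(110, q) ≤ 22)]²,

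with q = p under the protocol limit and q = p(1 − s) under the SAP limit.

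| p | Protocol limit | SAP limit, s = 0.10 | SAP limit, s = 0.25 | SAP limit, s = 0.50 |
|---|---|---|---|---|
| 0.10 | 0.1% | <0.1% | <0.1% | <0.1% |
| 0.15 | 11% | 4% | 0.5% | <0.1% |
| 0.20 | 69% | 43% | 11% | 0.1% |
| 0.25 | 98% | 90% | 53% | 2% |
| 0.30 | about 100% | about 100% | 90% | 11% |

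For example, with p = 0.20 and s = 0.25, q = 0.20 × 0.75 = 0.15, and the chance falls from 69% to 11%.

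**4. Values kept if the analysis runs**

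The expected number of subjects keeping a protocol-late value is 220 × p × s:

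- p = 0.20: 220 × 0.20 × 0.25 = 11, and 220 × 0.20 × 0.50 = 22.
- p = 0.30: 220 × 0.30 × 0.25 = 16.5, and 220 × 0.30 × 0.50 = 33.

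**The case against.** **Which number is the error cannot be proved.** The SAP was written on protocol version 1, which is not available here; the protocol at hand is version 2.0. Its change list mentions no alteration to the follow-up windows, but it does include minor editorial updates, so its silence is suggestive and not conclusive. This stands: the origin of 223 is unknown. It does not remove the conflict with the protocol in force.

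**The trigger sentence does not itself define late.** Day 224 comes from the carry-forward rule that follows. That is fair, but it is the only definition the section offers, and the carry-forward rule is explicit on any reading.

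**The probabilities depend on chosen inputs.** This also stands. If 10% or fewer visits are late by the protocol, the trigger hardly ever fires under either limit, and the discrepancy barely touches it. The figures also describe one of two triggers, so they are not the probability that Sensitivity Analysis 3 is missed.

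**Other safeguards exist.** The Wilcoxon trigger ignores the window and addresses a timing difference between arms, arguably the more harmful kind. Days to the 6-month assessment are summarised by arm unconditionally, and out-of-window visits are reported as deviations. These limit the harm, but none of them re-analyses the endpoint within the protocol's window.

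**Conclusion.** The concern holds. The SAP and the current protocol disagree by 12 days on when the 6-month window closes, and the SAP presents its figure as the protocol's. As written, Sensitivity Analysis 3 cannot test its stated aim, and its late-visit trigger is less sensitive than the protocol's window implies.

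The mismatch and the count of 23 late visits per arm need no assumption beyond 110 subjects per arm. The size of the effect on the trigger does depend on the assumed late rate and timing: negligible at a 10% late rate, and large at 20% to 25% if a quarter or more of late visits fall on days 212 to 223.

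The primary analysis, its type I error and the sample size are unchanged. This is a correction that should be made; it does not threaten the main result.

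**What to change.** In SAP 6.2.2.4 change 223 to 211, and in 6.2.2.9 change 224 to 212. If day 223 was intended, reconcile Table 6 of the protocol instead and record the reason. Either way, state in the trigger sentence which day makes a visit late.

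Check the same limits in the CCS derivation program, since 6.2.2.4 says it was adapted for this study's visit windows and it may carry the same figure. Settle this before results by arm are known, so that the limit is not chosen after the fact.

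The cost is two numbers, one clarifying phrase and a check of the date limits in one program. No new data are needed.

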6.2.2.5 Determination of Subjects

The analysis of the primary endpoint for this study will be ITT.

6.2.2.6 Missing Data

The definition of the CCS ensures that no subject will have a missing value for the primary outcome. For example, if a subject is randomized and lost to follow-up immediately afterward, they will be classified as “unchanged” according to the algorithm defined above, and therefore “not improved” for the primary analysis. Precautions will be taken to ensure that every subject has a baseline NYHA classification prior to assignment of a treatment group, but if a subject without a baseline NYHA value is randomized despite these efforts, they will be included in the analysis of the primary endpoint with the conservative assumption that the subject was NYHA class II at baseline.

6.2.2.7 Sensitivity Analysis 1: Adjusting for Subject Gender and NYHA

To test the potential effect of differential distribution of NYHA class and subject sex among treatment groups, a sensitivity analysis will be done using a logistic regression model with randomization arm, gender and NYHA class as fixed effects, and site as the random effect. Sites with a low number of enrollments will be grouped into clusters according to methods outlined in section 6.3 (Center Pooling) below. Example SAS code is as follows:

```
proc glimmix data=analysis.secObj1;
class aCRT_ITT NYHA Sex site;
model CCS_Improved = aCRT_ITT NYHA Sex/ dist=bin link=logit solution;
random intercept / subject=site type = vc;
run;
```

It is noted that, under ideal circumstances, the p-value based on the resulting score test would be used in this case, as that is the direct analog to the chi-square test in the ITT analysis, rather than the more powerful test based on the Wald estimator provided by Proc Glimmix in SAS (see sample size simulations available under separate cover). Should Proc Glimmix fail to converge on parameter estimates, the equivalent model specification will be fit using the nlme package in R. If that also fails to converge, a conditional logistic regression model will be used instead (i.e., SAS Proc Logistic with site

specified in a strata statement). This sensitivity analysis will be performed in the ITT dataset; subjects who cross over and subjects treated in violation of major inclusion/exclusion criteria will still be analyzed according to their assigned randomization.

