Study Design and Scope	
The Mid-Q Response study is a prospective, multi-center, randomized controlled, interventional, single-blinded, post-market study. The study will be executed at approximately 60 centers in Asia including but not limited to centers in Japan, South Korea, Taiwan, Hong Kong, Indonesia, Malaysia, Singapore, Brunei, the Philippines, and China.
 
Study flow:
 <pre> graph TD     A[NYHA II-III-IV, LVEF≤35%, LBBB, PR ≤200 ms, QRS >120 ms and < 150ms] --> B[ICF, Eligibility Criteria, Baseline assessment]     B --> C[Implant CRT-P or CRT-D with AdaptivCRT]     C --> D[Randomization 1:1]     D --> E[aCRT ON (Adaptive Bi-V and LV)]     D --> F[aCRT OFF (Nonadaptive CRT)]     E --> G[3, 6 and 12 month Follow-ups]     F --> G     G --> H[Primary endpoint: Clinical Composite Score @ 6 months]     G --> I[Study complete @ 12 months]   </pre>
Randomization	
The subjects will be randomly assigned in a 1:1 ratio to the aCRT ON (Adaptive Bi-V and LV) group or the aCRT OFF (Nonadaptive CRT) group.

Sample Size	A total of 220 randomized patients followed through 6 months are needed for the study primary analysis. To achieve this, we expect to need 232 enrolled patients. A maximum of 50 randomized patients is allowed at each site.

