### 12.3.2. Hypothesis and Analysis Methods

The null-hypothesis that will be tested is that the proportion of patients with Improved CCS is not different between the randomized arms:

$$H_0: p_{aCRT} = p_{control}$$

$$H_A: p_{aCRT} \neq p_{control}$$

The analysis will use a Chi-square test comparing the proportion Improved between randomized arms. The null-hypothesis will be rejected when the p-value is < 0.05. It will be concluded that aCRT is associated with a higher proportion Improved in case the null-hypothesis is rejected and the proportion Improved is higher in the aCRT ON arm.

A sensitivity analysis may be done using a logistic regression model with randomized arm, gender and NYHA class as fixed effects and site as random effect. Sites with a low number of enrollments will be grouped into clusters.

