### 12.4.2. Sample Size Assumptions

- The CRT arms from MIRACLE and REVERSE have CCS Improved in 67% and 55% of the patients. It is assumed that this represents the difference between NYHA classes II and III, and that the corresponding OR = 1.66 will be the same for both arms of the Mid-Q Response study.
- Based on the Adaptive CRT trial results, it is conservatively assumed that CCS would be Improved for 59% of the NYHA III patients in the regular CRT control arm. Applying the OR =

1.66 for NYHA III vs II would give a CCS Improved rate of 46% for NYHA class II patients with regular CRT.

- Similarly, the percentage improved for NYHA II patients in the AdaptivCRT arm would be 69%, compared to 79% for the NYHA III patients.
- The expected enrollment in the Mid-Q Response study is 55% NYHA class III and 45% NYHA class II, so that the overall CCS Improved rate will be 53% in the regular CRT arm and 75% in the AdaptivCRT arm. To add conservatism, for sample size calculation, the rate in the regular CRT arm is raised to 55%.
- Assuming CCS is improved in 75% of patients in the AdaptivCRT arm and in 55% of patients in the regular CRT arm, a minimum of 220 patients must be randomized to achieve a power of 80% to demonstrate a significant difference in presence of 3% crossover in both arms. Pre-randomization attrition is expected to be at most 5%, so that approximately 232 patients will be enrolled to fulfil the sample size requirements for the primary analysis. Up to 3% post-randomization drop out is expected; however, subjects who drop out post randomization contribute to primary objective because, by definition, CCS is not impacted by missing data.

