6.3 Center Pooling

Site will be included as a random effect in a sensitivity analysis of the primary endpoint to account for the site-by-site variability in the assessment. Descriptive statistics for the primary endpoint will be reported study-wide and by investigational sites. In the circumstance where the statistical model described in section 6.2.2.8 cannot converge due to low enrollments of some sites, sites with fewer than 5 randomized subjects will be combined, first to other small sites within country. If all small sites in a country still have fewer than 5 randomized subjects combined, they will be combined with the smallest site from that country with 5 or more subjects. For the study's final report, no formal assessments of country-to-country or site-to-site heterogeneity are planned, and data from all participating study centers will be pooled for all primary, secondary and ancillary objectives. For purposes beyond the final report, additional subsetting of any pre-specified analyses may be performed as needed if required by local regulatory authorities.

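### The pooling and non-convergence rules for Sensitivity Analysis 1 of the primary endpoint cannot all be followed, and the first fallback package does not fit the specified logistic model

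*SAP*

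**What the plan says.** The primary analysis is a chi-square test without site: "The null hypothesis will be rejected if the two-sided p-value is < 0.05" (SAP 6.2.2.4). The same section notes that randomization is blocked within sites and defers possible clustering effects to SAP 6.2.2.7.

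SAP 6.2.2.7 specifies a logistic model with arm, sex and NYHA class as fixed effects and a random site intercept, fitted in GLIMMIX with a binomial distribution and logit link. It says that small sites will be clustered by the methods of SAP 6.3. For non-convergence it gives two steps: "the equivalent model specification will be fit using the nlme package in R", and after a second failure "a conditional logistic regression model will be used instead", with site as the stratum. It says the analysis uses the ITT dataset.

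On pooling:

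- Protocol 12.3.2: "Sites with a low number of enrollments will be grouped into clusters". No condition is attached.
- SAP 6.3 attaches one: "In the circumstance where the statistical model described in section 6.2.2.8 cannot converge due to low enrollments of some sites". Sites with fewer than five randomized patients are then merged within country and, if the merged group is still below five, joined to that country's smallest site with five or more.

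SAP 6.2.2.8 is the per-protocol chi-square comparison. It has no site term.

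**The concern.** With 220 randomized patients, about 60 planned centers (Protocol 3.3) and no general minimum per center, sparse sites are likely. The SAP itself plans for non-convergence, so these rules may be needed. Three things go wrong when one tries to follow them.

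1. **Order.** Two texts pool before fitting and one pools only after a failed fit. For that same failure, SAP 6.2.2.7 gives a different sequence in which pooling has no place.
2. **Cross-reference.** SAP 6.3 ties pooling to a section that contains no model capable of failing to converge.
3. **Software.** The first fallback is called an equivalent specification, but the package named does not on its own fit a binomial mixed model. Used directly, it could return a converged linear fit to a 0/1 outcome, which might be reported as the planned logistic analysis.

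What is at stake is pre-specification. The definition of site, the model, and (at the last step) how many patients inform the treatment estimate would be settled after the data are known.

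**Working it through.** **The plan's own figure.** Inputs from Protocol 12.4.2 and the Synopsis: "Assuming CCS is improved in 75% of patients in the AdaptivCRT arm and in 55% of patients in the regular CRT arm"; 220 randomized "to achieve a power of 80% to demonstrate a significant difference in presence of 3% crossover in both arms"; 1:1 allocation; two-sided α = 0.05.

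- Crossover-diluted rates: 0.97 × 0.75 + 0.03 × 0.55 = 0.744, and 0.97 × 0.55 + 0.03 × 0.75 = 0.556.
- The two-proportion formula gives 99.9, so 100 per arm (200 in total) without continuity correction, and 110.2, so 111 per arm (222) with it. The plan has 220.
- Exact power at 110 per arm is 84.1% for Pearson's test and 80.2% with continuity correction.
- Enrollment: 220 / 0.95 = 231.6, so 232.

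The sample size is reproduced to within 2 patients. Nothing below changes it.

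**The rules side by side.**

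| Text | When small sites are pooled | What follows non-convergence |
|---|---|---|
| Protocol 12.3.2 | Always | Not stated |
| SAP 6.2.2.7 | Always, by the 6.3 methods | nlme, then conditional logistic regression |
| SAP 6.3 | Only after non-convergence of the model in 6.2.2.8 | Pooling |

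Rows 2 and 3 cannot both be followed. If pooling comes first, the trigger in 6.3 is redundant. If it waits for a failed fit, 6.2.2.7 is not followed, and nothing says whether pooling precedes nlme, follows it, or replaces it.

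**The software.** In R 4.3.3 with nlme 3.1.168, the package describes itself as fitting Gaussian linear and nonlinear mixed-effects models. Its lme function rejects a binomial family argument as unused. Without that argument it fits a linear model to the 0/1 outcome.

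**Why the order matters at the last step.** Conditional logistic regression stratified by site takes no treatment information from a stratum in which all outcomes are the same or all patients are in one arm. The documents give no figure for this loss.

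- Mean site size: 220 / 60 = 3.7 (Protocol), or 220 / 55 = 4.0 (SAP section 5).
- Hand check for a site of four, two per arm, with no site effect: 0.75² × 0.55² + 0.25² × 0.45² = 0.170 + 0.013 = 0.183. About 18% of such sites are uninformative.

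Simulation of 220 patients at 75% v 55% Improved, blocked within site. Assumed: blocks of 2 or 4, ten countries, and site sizes from equal to strongly skewed (multinomial, or gamma-weighted with shape 2, 1 or 0.5). Entries are mean shares of patients in uninformative strata.

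| Scenario | No between-site variation (single-outcome strata) | Site SD 0.5 on the logit scale (single-outcome or single-arm strata) |
|---|---|---|
| 60 enrolling sites, unpooled | 12–22% | 13–24% |
| 40 enrolling sites, unpooled | 7–10% | 8–13% |
| Pooled by the 6.3 rule | 0–5% (55–60 sites) | 2–6% (uneven site sizes) |

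Pooling helps only where sites fall below the threshold. With 40 sites of equal size, each has five or six patients, nothing is pooled, and the share stays at 9.2% with no between-site variation.

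**The case against.** The case against runs as follows.

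- **SAP 6.2.2.7 adopts 6.3 rather than competing with it, and the Protocol sentence is a general remark about an analysis that may be done.** This narrows the problem to one of ordering. It does not remove it, because the section adopted carries the opposite trigger.
- **The reference to 6.2.2.8 is a slip.** Agreed. A reader might infer that pooling can never be triggered. The documents do not support that: SAP 6.3 opens by describing a random site effect in a sensitivity analysis of the primary endpoint, which can only be 6.2.2.7.
- **An nlme-based logistic fit exists.** MASS::glmmPQL uses nlme as its engine and fits a binomial random-intercept model. The SAP does not name it, and nlme called directly does something else, so the wording still needs correcting.
- **The last fallback is remote.** It follows two failed fits, and no probability of reaching it can be derived from the documents. This stands and limits the weight of the percentages.
- **Losing strata does not breach ITT.** SAP 6.2.2.7 uses the label to mean analysis by assigned arm, which uninformative strata do not alter. Single-arm strata with mixed outcomes also still inform the sex and NYHA coefficients. It is fair to say that these patients contribute nothing to the treatment estimate, but not that all of them are discarded.
- **Departures from the SAP must be explained in the final report (SAP 6.8).** True, but explaining a choice afterwards does not pre-specify it.

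**Conclusion.** The point holds as a defect of specification in a supportive analysis. The pooling order conflicts between SAP 6.2.2.7 and Protocol 12.3.2 on one side and SAP 6.3 on the other; the cross-reference in 6.3 is wrong; and nlme as named does not fit the specified model. None of the three depends on simulation.

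The size is conditional. If conditional logistic regression is reached, the share of patients giving no treatment information is about 13–24% with 60 enrolling sites unpooled, about 8–13% with 40 unpooled, and about 2–6% with 6.3 pooling. These figures rest on assumed site sizes, block sizes, between-site variation and ten countries. A reader might take the upper range as a fixed loss of up to a quarter of the patients. The documents do not support that, because 6.2.2.7 as written pools first and the number of enrolling sites is unknown.

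Nor does the point reach the primary chi-square test, its success rule or N = 220. It does not show that pooling or conditional logistic regression is wrong in itself; keeping or dropping either is a design choice. The change should be made, but it is not critical.

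**What to change.** 1. State one ordered rule in SAP 6.2.2.7 and 6.3, consistent with Protocol 12.3.2. For example: pool sites with fewer than five randomized patients first, then fit the model, then go to the fallbacks in sequence.
2. Correct the reference in SAP 6.3 from 6.2.2.8 to 6.2.2.7.
3. Replace nlme with a function that fits a binomial mixed model, for example lme4::glmer, or MASS::glmmPQL if an nlme-based fit is wanted.
4. If conditional logistic regression is used, report the number of patients in strata that give no treatment information.

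The cost is SAP wording only. An order that pools first needs no Protocol amendment, and there is no cost in data or patients.
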